7.1.2 Definition of Study Days

When calculating Study Day relative to a reference date (ie, date of first dose of double-blind study drug [Day 1]), if the date of the observation is on the same date or after the reference date, it will be calculated as: date of observation - reference date + 1; otherwise, it will be calculated as: date of observation - reference date. Hence, reference day is always Day 1 and there is no Day 0.

When calculating Follow-up Day relative to a reference date (ie, date of last dose of double-blind study drug [Follow-up Day 0]), it will be calculated as: date of observation - reference date. Hence, reference day is always Follow-up Day 0.

7.1.3 Definition of Study Visit Windows

All evaluable data (ie, non-missing and acceptable according to the Handling Rules for Analysis Data) will be handled according to the following rules.

For each visit, observation obtained in the corresponding time interval will be used. If more than one observation lies within the same visit window, the observation with the closest Study Day to the scheduled Study Day will be used. If there are two observations equidistant to the scheduled Study Day, the later observation will be used.

Transvaginal ultrasound and UFS-QOL score

Visit	Scheduled Study Day (days)	Time Interval (days)	
		Study Day	Follow-up Day
Baseline	Study Day: 1	-80 - 1	
Week 12	Study Day: 85	2 - 99	< 4

Pharmacodynamic measurements

Visit	Scheduled Study Day (days)	Time Interval (days)	
		Study Day	Follow-up Day
Baseline	Study Day: 1	-80 - 1	
Week 4	Study Day: 29	2 - 43	< 4

Visit	Scheduled Study Day (days)	Time Interval (days)	
		Study Day	Follow-up Day
Week 8	Study Day: 57	44 – 71	< 4
Week 12	Study Day: 85	72 – 99	< 4
Follow-up	Follow-up Day: 28	2 <=	4 – 42

Clinical laboratory tests and Vital sign and Weight

Visit	Scheduled Study Day (days)	Time Interval (days)	
		Study Day	Follow-up Day
Baseline	Study Day: 1	-80 - 1	
Week 4	Study Day: 29	2 – 43	< 15
Week 8	Study Day: 57	44 – 71	< 15
Week 12	Study Day: 85	72 – 99	< 15
Follow-up	Follow-up Day: 28	2 <=	15 – 42

12-lead ECG

Visit	Scheduled Study Day (days)	Time Interval (days)	
		Study Day	Follow-up Day
Baseline	Study Day: 1	-80 - 1	
Week 12	Study Day: 85	2 – 99	< 15
Follow-up	Follow-up Day: 28	2 <=	15 – 42

7.1.4 Methods for Handling Missing Data

All available efficacy and safety data will be included in data listing and tabulations. No imputation of values for missing data will be performed unless otherwise specified.

- For UFS-QoL, published scoring manuals and guidelines will be used to calculate UFS-QoL and handle missing data (see Appendix 3).
- For myoma or uterus volume, if D1 and D2 of the myoma or uterus are present but D3 is missing, then the volume will be calculated as $D1*D2*D2*\pi/6$ (cm^3).
- For LH, FSH, E₂, P and clinical laboratory tests, values less than the lower limit of quantification will be treated as zero when calculating the descriptive statistics.

- Disease duration with first diagnosis date of uterine fibroid that are completely or partially missing will be derived as follows:
 1. If the year is missing, then the disease duration will be treated as missing.
 2. If the year is present but the month is missing, then the month will be treated as January for the calculation.

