TAK-385 has been synthesized at Takeda Pharmaceutical Company Limited (TPC) and is an orally active, nonpeptide, GnRH antagonist with a novel structure. TAK-385 antagonizes GnRH on the GnRH receptors that are present in the pituitary anterior lobe basophiles (secretory cells), and inhibits the GnRH-stimulated secretion of luteinizing hormone (LH) and follicle-stimulating hormone (FSH) from these cells. As a result, the drug decreases blood concentrations of hormones, including estradiol (E₂) and progesterone (P), and induces amenorrhea. Therefore, TAK-385 is expected to improve the clinical symptoms observed in patients with uterine fibroids. As TAK-385 is a GnRH antagonist, it causes no flare up and has a faster onset of action than GnRH agonists. Unlike GnRH agonists, which are given either subcutaneously (SC) or intranasally, TAK-385 is a nonpeptide preparation and can be administered orally.

For the above reasons, the development of TAK-385 for the treatment of benign sex hormone-dependent gynecological diseases, such as endometriosis and uterine fibroids, has been progressing in Japan and overseas.

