5.1.3 Additional Objectives

An additional objective of this study is to evaluate the pharmacodynamic effect, which is blood concentrations of LH, FSH, E₂, and P.

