7.0 METHODS OF ANALYSIS AND PRESENTATION

7.1 General Principles

All statistical analyses will be conducted using SAS® Version 9.2, or higher.

A statistical test for the primary endpoint will be reported as 2-sided and will be assessed at $\alpha=0.05$ significance level and all confidence intervals will be reported as 2-sided unless otherwise stated. P-values will be rounded to 4 decimal places prior to assessment of statistical significance.

Means and medians will be presented to 1 more decimal place than the recorded data. The standard deviations (SDs) will be presented to 2 more decimal places than the recorded data. Confidence intervals about a parameter estimate will be presented using the same number of decimal places as the parameter estimate.

Where appropriate, variables will be summarized descriptively by study visit. For the categorical variables, the count and proportions of each possible value will be tabulated by treatment group. The denominator for the proportion will be based on the number of subjects who provided non-missing responses to the categorical variable. For continuous variables, the number of subjects with non-missing values, mean, median, SD, minimum, and maximum values will be tabulated. Confidence intervals for continuous variables will be calculated based on t-statistics and ones for categorical variables will be based on Wald confidence intervals without using any model, unless otherwise stated.

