7.9.2 Pharmacodynamic Analysis

7.9.2.1 LH, FSH, E₂, and P

Analysis Set: Full Analysis Set

Analysis

Variable(s) : LH
FSH
E₂
P

Visit: Baseline , Week 4, 8, 12 and Follow-up

Analytical

Method(s) : For each variable, summaries (1) and (2) will be provided by treatment group.

- (1) Summary of each variable and Change from Baseline by Visit.
Descriptive statistics for observed values for each visit and changes from baseline will be provided.
- (2) Case Plots
Plots over time for each subject will be presented.

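### Setting LH, FSH, E₂ and P values below the quantification limit to zero biases the visit means downward and can overstate suppression; the plan gives no count of such values

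*SAP*

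**What the plan says.** SAP 7.1.4 (Methods for Handling Missing Data) covers LH, FSH, E₂, P and the clinical laboratory tests in one rule: "values less than the lower limit of quantification will be treated as zero when calculating the descriptive statistics". This point concerns the four hormones.

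SAP 7.9.2.1 plans two hormone outputs by treatment group for baseline, Weeks 4, 8 and 12, and Follow-up. The first is a summary: "Descriptive statistics for observed values for each visit and changes from baseline will be provided". The second is a set of individual case plots. For continuous variables in general, SAP 7.1 says that "the number of subjects with non-missing values, mean, median, SD, minimum, and maximum values will be tabulated". Quartiles and a count of values below LLOQ are not on that list.

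The hormones serve the one additional objective in Protocol 5.1.3: "An additional objective of this study is to evaluate the pharmacodynamic effect". Protocol 4.1 describes the expected direction. TAK-385 "inhibits the GnRH-stimulated secretion of luteinizing hormone (LH) and follicle-stimulating hormone (FSH) from these cells", and as a result "the drug decreases blood concentrations of hormones, including estradiol" and progesterone.

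**The concern.** A result below LLOQ is known only to lie between 0 and LLOQ. The rule places all such results at the bottom of that interval. The drug is meant to move hormone values towards that interval, so the rule is likely to act most where the effect is being measured. How strong the suppression looks then depends partly on a substitution constant.

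The planned tables would not reveal this. A minimum or median of 0 would look like an observed value, and no row shows how many results were censored. The descriptive tables and case plots are the whole planned analysis for the pharmacodynamic objective, so no second analysis would correct the impression. The rule covers descriptive statistics only, and the SAP does not say how censored values appear in the case plots.

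**Working it through.** The plan states no figure on this point, so there is none to reproduce. The documents give no LLOQ, no expected censored share and no hormone mean or SD. Everything below is therefore algebra, or an illustration in units of LLOQ under stated assumptions.

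**Visit mean.** Let f be the share of values below LLOQ and c their true mean, with 0 ≤ c < LLOQ.

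- Bias of the reported mean = −f × c, which lies between 0 and −f × LLOQ.
- It is never upward, and it cannot exceed the true mean in size, because the true mean is f × c plus (1 − f) times the mean of the quantified values.

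**Relative size (assumed lognormal values, log-SD 0.5 to 1.2).** As one worked case, take log-SD 0.5 and f = 50%. The true mean is 1.133 LLOQ and c = 0.699 LLOQ. The reported mean is 1.133 − 0.5 × 0.699 = 0.784 LLOQ, a bias of −31%. Setting the censored values to LLOQ gives 0.784 + 0.5 = 1.284 LLOQ, so the two substitutions bracket the true mean. Over the range of log-SDs:

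| Share below LLOQ | Set to 0 | Set to LLOQ/2 | Set to LLOQ |
|---|---|---|---|
| 5% | −0.2% to −1.6% | −0.6% to −0.1% | +0.1% to +0.3% |
| 30% | −4% to −15% | −5% to −0.3% | +4% to +5% |
| 50% | −12% to −31% | −9% to +1% | +13% to +15% |
| 70% | −25% to −51% | −11% to +7% | +29% to +39% |
| 90% | −53% to −78% | −3% to +49% | +73% to +151% |

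**Other statistics.** One censored value makes the minimum 0. The median is unaffected while fewer than half the values are censored, and is 0 when more than half are.

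**Contrast between arms.** Suppose a reader subtracts the TAK-385 mean from the placebo mean at a visit. With T for TAK-385 and P for placebo, suppression is overstated by fT × cT − fP × cP. Each c can lie anywhere between 0 and LLOQ, so the range is −fP × LLOQ to +fT × LLOQ. With an assumed c = 0.5 LLOQ in both arms:

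- fT = 50%, fP = 5%: 0.250 − 0.025 = 0.225 LLOQ overstated (range −0.05 to +0.50).
- fT = 90%, fP = 5%: 0.450 − 0.025 = 0.425 LLOQ overstated (range −0.05 to +0.90).
- fT = fP = 70%: 0.

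**Change from baseline within an arm.** Bias = f_base × c_base − f_post × c_post, where a negative value overstates the fall. With c = 0.5 LLOQ at both times:

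| f_base | f_post | Bias (× LLOQ) |
|---|---|---|
| 0% | 50% | −0.25 |
| 30% | 50% | −0.10 |
| 50% | 50% | 0 |
| 70% | 50% | +0.10 |

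**The case against.** The best defence has four parts.

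1. **Nothing inferential depends on the rule.** The hormones are an additional endpoint. SAP 7.9.2.1 plans no between-arm difference, confidence interval or test for them, although SAP 7.8.2.1 and 7.8.3.1 do specify differences for other endpoints. The only planned test is the one described in SAP 7.1: "A statistical test for the primary endpoint will be reported as 2-sided". This stands, and it limits the point to an improvement in reporting.

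2. **The direction is not fixed.** A reader might infer that the rule always favours the drug. The documents do not support that. Baseline values are zeroed as well, so the bias in change from baseline can vanish or reverse, as shown above.

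3. **More censoring on TAK-385 is an inference.** A reader might also infer that placebo is almost untouched. Protocol 4.1 makes heavier censoring on TAK-385 likely but gives no shares. Both arms give the baseline sample on days 1 to 5 of menstruation (Protocol 9.3.2.1). Later treatment visits are 28 days apart, which is the average cycle length in Protocol 6.2.3.1, so many placebo samples may fall in a similar phase. Whether any hormone is then below LLOQ is unknown and may differ by hormone.

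4. **The rule is pre-stated and the same for both arms, and part of the remedy exists.** The median is already planned, SAP 7.1.4 puts all available data in listings, and LLOQ/2 is not unbiased either. All of this is true. But the median helps only while fewer than half the values are censored. A tabulated 0 hints at censoring without giving its extent. The bias of LLOQ/2 is a reason to show bounds, not to keep zero alone.

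**Conclusion.** The concern holds in a limited form. Any hormone visit mean that includes censored values is biased downward by f × c, which is less than f × LLOQ. This follows from the rule alone. That on-treatment means can overstate suppression rests on one inference, namely that a drug expected to lower all four hormones produces more censored values in its own arm. For change from baseline the direction depends on how much is censored at baseline.

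The size cannot be fixed from the documents. In the lognormal illustration the bias is negligible at 5% censored (at most 1.6% of the mean) and large at 90% (53% to 78%). A large relative bias arises only where the true mean is already near or below LLOQ, so a reader should not take the illustration to show that the drug's suppression is an artefact. The primary test, alpha, power and efficacy conclusion are unaffected.

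**What to change.** In SAP 7.1.4 and 7.9.2.1, for LH, FSH, E₂ and P:

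- State the LLOQ of each assay.
- Report n (%) below LLOQ by arm and visit, including baseline.
- Add quartiles to the median, and print `<LLOQ` wherever the quantile is censored.
- Give each visit mean twice, with censored values set to 0 and to LLOQ. The two figures bracket the mean that full quantification would give, with no distributional assumption.

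The cost is some SAP wording and a few extra rows per hormone table. No new data are needed and the primary analysis is untouched. Suppression may look slightly less favourable than under zero substitution alone.

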7.2 Analysis Sets

Refer to the Handling Rules for Analysis Data.

7.3 Disposition of Subjects

7.3.1 Study Information

Analysis Set: All Subjects Who Signed the Informed Consent Form

Analysis

Variable(s) : Date first subject signed informed consent form
Date of last subject's last visit/contact
MedDRA Version
WHO Drug Version
SAS Version used for creating the datasets

Analytical

Method(s) : (1) Study Information
Study information shown in the analysis variables section will be provided.

7.3.2 Screen Failures

Analysis Set: All Subjects Who Were Not Randomized

Analysis

Variable(s) : Age (years) [20<= - <30, 30<= - <40, 40<= - <50, 50<= - <=Max]

Analytical

Method(s) : (1) Screen Failures
Frequency distributions for categorical variables and descriptive statistics for continuous variables will be provided.

7.3.3 Subject Eligibility

Analysis Set: All Subjects Who Signed the Informed Consent Form

Analysis

Variable(s) :	Eligibility Status	[Eligible for Randomization, Not Eligible for Randomization]
	Primary Reason for Subject Not Being Eligible	[Death, Adverse Event, Screen Failure, Protocol Deviation, Lost to Follow-up, Withdrawal by Subject, Study Terminated by Sponsor, Pregnancy, Other]

Analytical

Method(s) : (1) Eligibility for Randomization

Frequency distributions will be provided. When calculating percentages for the primary reasons for subject not being eligible, the total number of ineligible subjects will be used as the denominator.

7.3.4 Number of Subjects Randomized by Site and Treatment Group

Analysis Set: Randomized Set

Analysis

Variable(s) :	Randomization Status	[Randomized]
Stratum:	Site	[Site numbers will be used as categories]

Analytical

Method(s) : (1) Number of Subjects Randomized by Site and Treatment Group
Frequency distribution will be provided for each stratum by treatment group and overall.

7.3.5 Disposition of Subjects

Analysis Set: Randomized Set

Analysis Double-Blind Study Drug

Variable(s) :	Administration Status	[Randomized but Not Treated]
	Reason for Not Being Treated	[Death, Adverse Event, Protocol

CONFIDENTIAL

	Deviation, Lost to Follow-up, Withdrawal by Subject, Study Terminated by Sponsor, Pregnancy, Lack of Efficacy, Other]
Double-Blind Study Drug	[Completed Study Drug, Prematurely Discontinued Study Drug]
Completion Status	
Reason for Discontinuation of Study Drug	[Death, Adverse Event, Protocol Deviation, Lost to Follow-up, Withdrawal by Subject, Study Terminated by Sponsor, Pregnancy, Lack of Efficacy, Other]
Completion Status of the Follow- up Period	[Completed Follow-up Period, Prematurely Discontinued Follow- up Period]
Reason for Discontinuation of the Follow-up Period	[Death, Adverse Event, Protocol Deviation, Lost to Follow-up, Withdrawal by Subject, Study Terminated by Sponsor, Pregnancy, Lack of Efficacy, Other]
Analytical Method(s) :	
(1) Disposition of Subjects
 
Frequency distributions will be provided for each treatment group and overall. When calculating percentages for the reasons for not being treated, the total number of subjects not treated by the study drug will be used as the denominator. When calculating percentages for the reasons for discontinuation, the total number of subjects who prematurely discontinued will be used as the denominator.

7.3.6 Protocol Deviations

Analysis Set: Randomized Set

Analysis

Variable(s) : Protocol Deviation [Major GCP Violations, Deviations of Protocol Entry Criteria, Deviations of Discontinuation Criteria, Deviations Related to Treatment Procedure or Dose, Deviations Concerning Excluded Medication or Therapy, Deviations to Avoid Emergency Risk]

Analytical

Method(s) : (1) Protocol Deviations

Frequency distribution will be provided by treatment group and overall for each deviation category. A subject who has several deviations will be counted once in each appropriate category. A subject who has several deviations that can be classified into the same category will be counted only once.

7.3.7 Analysis Sets

Analysis Set: Randomized Set

Analysis

Variable(s) : Handling of Subjects and Subject Data [Categories are based on the specifications in Handling Rules for Analysis Data]

Analysis Sets

Full Analysis Set	[Included]
Per Protocol Set	[Included]
Safety Analysis Set	[Included]

Analytical

Method(s) : (1) Subjects Excluded from Analysis Sets
(2) Subject Data Excluded from Analysis Sets
(3) Analysis Sets

Frequency distributions will be provided by treatment group for (1) and

(2), and by treatment group and overall for (3). For (1) and (2), a subject who has several reasons for exclusion will be counted once in each appropriate category. A subject who has several reasons for exclusion that can be classified into the same category will be counted only once.

7.4 Demographic and Other Baseline Characteristics

Analysis Set: Randomized Set

Analysis

Variable(s) :	Age (years)	[20<= - <30, 30<= - <40, 40<= - <50, 50<= - <=Max]
	Height (cm)	[Min<= - <150, 150<= - <160, 160<= - <170, 170<= - <=Max]
	Weight (kg) at Baseline	[Min<= - <50, 50<= - <60, 60<= - <70, 70<= - <80, 80<= - <=Max]
	BMI (kg/m ²) at Baseline	[Min<= - <18.5, 18.5<= - <25.0, 25.0<= - <=Max]
	Smoking Classification	[The subject has never smoked, The subject is a current smoker, The subject is an ex-smoker]
	Birth Experience	[Yes, No]
	Disease Duration (years)	[Min<= - <=1, 1< - <=3, 3< - <=5, 5< - <=10, 10< - <=Max]
	Type of Uterine Fibroid	
	Subserosal Fibroid	[Yes, No]
	Intramural Fibroid	[Yes, No]
	Submucosal Fibroid	[Yes, No]
	Cervical Fibroid	[Yes, No]
	Stopped Any Medications for Uterine Fibroids	[Yes, No]
	Type of Medication for Uterine Fibroid	
	GnRH Agonist	[Yes]
	Herbal Medicine	[Yes]
	Other Medicines for	

UterineFibroids	[Yes]
Any Surgery for Uterine Fibroids	[Yes, No]
Volume of Myoma at Baseline (cm ³)	[Min<= - <=28, 28< - <=170, 170< - <=700, 700< - <=Max]
Volume of Uterus at Baseline (cm ³)	[Min<= - <=28, 28< - <=170, 170< - <=700, 700< - <=Max]
Maximum NRS Score at Baseline	[4<= - <7, 7<= - <=Max]
UFS-QOL Score at Baseline	
Symptom Severity	[Min<= - <=25, 25< - <=50, 50< - <=75, 75< - <=Max]
Concern	[Min<= - <=25, 25< - <=50, 50< - <=75, 75< - <=Max]
Activities	[Min<= - <=25, 25< - <=50, 50< - <=75, 75< - <=Max]
Energy/Mood	[Min<= - <=25, 25< - <=50, 50< - <=75, 75< - <=Max]
Control	[Min<= - <=25, 25< - <=50, 50< - <=75, 75< - <=Max]
Self-consciousness	[Min<= - <=25, 25< - <=50, 50< - <=75, 75< - <=Max]
Sexual Function	[Min<= - <=25, 25< - <=50, 50< - <=75, 75< - <=Max]
HRQL Total	[Min<= - <=25, 25< - <=50, 50< - <=75, 75< - <=Max]

Analytical

Method(s) : (1) Summary of Demographics and Baseline Characteristics
Frequency distributions for categorical variables and descriptive statistics for continuous variables will be provided by treatment group and overall.

7.5 Medical History and Concurrent Medical Conditions

Analysis Set: Safety Analysis Set

Analysis

Variable(s) : Medical History
Concurrent Medical Conditions

Analytical

Method(s) : (1) Medical History by System Organ Class and Preferred Term

CONFIDENTIAL

(2) Concurrent Medical Conditions by System Organ Class and Preferred Term

Frequency distributions will be provided for each treatment group.

MedDRA dictionary will be used for coding. Summaries will be provided using SOC and PT, where SOC will be sorted alphabetically and PT will be sorted in decreasing frequency.

A subject with multiple occurrences of medical history or concurrent medical condition within a SOC will be counted only once in that SOC.

A subject with multiple occurrences of medical history or concurrent medical condition within a PT will be counted only once in that PT.

7.6 Medication History and Concomitant Medications

Analysis Set: Safety Analysis Set

Analysis

Variable(s) : Medication History

Concomitant Medications

Analytical

Method(s) : (1) Medication History by Preferred Medication Name

(2) Concomitant Medications That Started Prior to and Were Ongoing at Baseline as well as Those That Started After Baseline by Preferred Medication Name

Frequency distributions will be provided for each treatment group. WHO Drug dictionary will be used for coding. Summaries will be provided using preferred medication names and sorted in decreasing frequency based on the number of reports. A subject who has been administered several medications with the same preferred medication name will be counted only once for that preferred medication name.

7.7 Study Drug Exposure and Compliance

Analysis Set: Safety Analysis Set

Analysis Duration of Exposure to Double- [1<= - <=14, 15<= - <=42,

Variable(s) : Blind Study Drug (days) 43<= - <=84, 85<= - <= Max]

Double-Blind Study Drug	[Min<= - <80, 80<= - <90, 90<= - <=Max]
Compliance (%)	<=Max]
Maximum Drug Holidays (days)	[0, 1<= - <4, 4<= - <=Max]

Analytical

Method(s) : (1) Study Drug Exposure and Compliance

Frequency distributions for categorical variables and descriptive statistics for continuous variables will be provided by treatment group and overall.

7.8 Efficacy Analysis

7.8.1 Primary Efficacy Endpoint(s)

7.8.1.1 Primary Analysis

Analysis Set: Full Analysis Set

Analysis

Variable(s): Proportion of subjects with a maximum NRS score of 1 or less during the 28 days before the final dose of study drug

Analytical

Method(s): The proportion of subjects with a maximum NRS score of 1 or less during the 28 days before the final dose of study drug will be summarized by treatment group. The primary analysis will be based on the comparison between the treatment groups using a Fisher's exact test. The point estimate and 2-sided 95% confidence interval of odds ratio will be calculated between TAK-385 40 mg group and placebo group (TAK-385 40 mg group / placebo group).

